9.1.2. PrEP provision and adherence counseling

The clinic will dispense PrEP and women will be counseled per South African national guidelines including about the importance of high PrEP adherence to achieve high levels of HIV protection, frequency, type and timing of side effects with oral FTC/TDF, and strategies for confidential storage and anticipating barriers to adherence. The clinic will also conduct HIV testing as needed. This is not a study-specific procedure: *the clinic will conduct PrEP prescribing, and HIV testing procedures separately from these study-specific procedures.* Generally, at PrEP initiation visits, the clinic will dispense PrEP and counsel women per South African national guidelines, including about the importance of high PrEP adherence to achieve high levels of HIV protection, frequency, type and timing of side effects with oral FTC/TDF, and strategies for confidential storage and anticipated barriers to adherence.

With respect to urine POC and drug level feedback adherence counseling, all participants will be asked to provide a urine sample for the tenofovir (TFV) point-of-care (POC) assay as part of study specific procedures. Approximately 2-3 minutes after 3-4 drops of urine are placed on a urine test strip, a "control" line should appear. An additional "tenofovir test line" will appear only if a participant has TFV levels <1500 ng/mL indicative of no recent PrEP dosing. This threshold will be recorded on a study case report form (CRF) and will be used to provide drug-level feedback counseling at the Week 4 visit. Participants will be counselled on their results by a lay counsellor. Youth Friendship Bench SA counselors will provide participants with a counseling message corresponding with their TFV POC assay results as follows. These counseling messages were used in prior PrEP studies with AGYW^{31,34,113}.

Control line only (one line appears on test) Key message: It looks like you took a PrEP pill recently--you are doing great! Remember that taking one PrEP pill every day is needed for strong protection against HIV. How can we help you keep up the good

Control and tenofovir test line (two lines appear on test) Key message: It looks like you haven't been able to take the PrEP medication in the past few days. Is PrEP something that you are still interested in? If yes, how can we help you?

We are including the POC assay and drug-level feedback counseling in the SOC arm (as well as in the Youth Friendship Bench arm) so that we can isolate the effect of our Youth Friendship Bench SA above and beyond this assay. Also, we hypothesize that this drug-level feedback approach will help to ensure retention in the SOC arm.

9.1.3. Other sexual and reproductive health outcomes

AGYW in South Africa are eligible for PrEP during pregnancy and postpartum and face a high burden of common mental disorders during these periods.^{118,119} In addition, the Friendship Bench has been used to provide mental health services for pregnant and postpartum women in other African contexts.¹²⁰ We will enroll AGYW regardless of pregnancy or postpartum status and will continue providing study procedures to AGYW who become pregnant during follow-up. AGYW mental health service delivery will continue to be managed according to South African Adult Primary Care Guidelines.

We may learn of participant concerns about GBV and immediate risk of harm due to a violent partner. In accordance with this guidance, clinic staff will provide first line support using the LIVES model (Listen, Inquire about needs and concerns, Validate, Ensure safety, and Support) for all AGYW who report gender-based violence or fears about gender-based violence during a clinic visit, counseling session, qualitative interview, or data collection. Clinic staff will ask about violence in a private, confidential setting and provide processes for referring participants to other services (e.g., medical services, additional counseling or social work services, police and law enforcement). We will continue to follow and offer standard-of-care and Youth Friendship Bench SA services to all participants reporting GBV in this study.

9.2. Safety Monitoring

Close cooperation between the Protocol co-Chairs and other study team members will be necessary in order to monitor participant safety and to respond to occurrences of SAEs in a timely manner. The study investigators are responsible for continuous close monitoring and management of SAEs.

9.3. Adverse Event Definition and Reporting

For the purposes of this study, only serious adverse events (SAEs) and adverse events of special interest (AESIs) will be recorded. These will be summarized by arm, as a secondary outcome of our study. SAEs are defined as those events that result in death, are life-threatening, require inpatient hospitalization or prolongation of existing hospitalization, and/or result in persistent or significant disability/incapacity. AESIs are considered reports of self-harm or self-injury.

With appropriate permission of the participant, whenever possible, records from all non-study medical providers related to SAEs will be obtained and required data elements will be recorded

on study CRFs. All participants reporting an AE will be followed clinically, until the AE resolves (returns to baseline) or stabilizes.

Site staff will also report information regarding SAEs to their IRB or other local regulatory agencies in accordance with all applicable regulations and local IRB requirements.

9.4. Social Impact Reporting

It is possible that participants' involvement in the study could become known to others, and that a social impact may result (i.e., because participants could be perceived as having a stigmatizing mental health condition, being HIV-infected, or at "high risk" for HIV infection). For example, participants could be treated unfairly, or could have problems being accepted by their families and/or communities. These are social harm events. Social harm events are those negative events that a participant reports as affecting them as a result of being involved in a research study. A social harm that is reported by the participant and judged by the study staff to be serious or unexpected will be reported to the site's IRBs at least annually, or according to local requirements.

In the event that a participant reports a social harm, every effort will be made by study staff to provide appropriate care and counseling to the participant as necessary, and/or referral to appropriate resources for the safety of the participant. While maintaining participant confidentiality, the site may engage the Youth Community Advisory Board (YCAB) in exploring the social context surrounding instances of social impacts, to minimize the potential occurrence of such an impact.

9.5. Study Oversight

The study will establish a Data Safety Monitoring Board (DSMB) to review data relating to safety and to ensure the continued scientific validity and merit of the study, according to the National Institute for Mental Health Data Safety Monitoring Board Operations Manual and a DSMB Charter to be established for this protocol. We will hold one DSMB meeting prior to study activation and enrollment to review study procedures and the statistical analysis plan and one after we enroll at least 50% of study participants to review preliminary data on enrollment characteristics including information on referrals for additional mental health services, retention, and social impact or SAE reporting. Other meetings will be held on an ad hoc basis.

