psychotherapy or pharmacotherapy as needed. We will also inform these AGYW that they can continue to receive PrEP at the study clinic.

Suicidal ideation, regardless of SRQ-20 score: The SRQ-20 includes one question on suicidal ideation ("Has the thought of ending your life been on your mind"), and anyone who endorses this item (regardless of their total SRQ-20 score) will be asked a series of three additional questions to determine suicidal intent ("Do you ever have thoughts of hurting or killing yourself?", "Are you currently thinking of killing yourself?", "Have you ever tried to kill yourself?"). They will also be provided referral to a social worker for further support as needed. Anyone who expresses suicidal intent or is deemed a risk to themselves or others will be ineligible for participation and immediately linked to inpatient care. They will only be able to re-screen into the study if and when their symptoms have stabilized and they not longer report self-harm or suicidal intent.

Worsening symptoms of common mental disorders throughout study follow-up: All participants will be asked whether their symptoms of common mental disorders have changed during the Week 4 and 12 visits and they will also complete the SRQ-20 at these time points. We will follow similar procedures as described for items a-c above, to ensure that individuals are linked with standard-of-care services regardless of SRQ-20 score. Those with symptoms of severe mental health distress or psychosis (e.g., unmanaged somatic symptoms, suicidal intent) will be linked to care and the study team will consider early termination from the study on a case-by-case basis.

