11.0 STATISTICAL CONSIDERATIONS

11.1. Review of Study Design

At enrollment, women will be randomized 1:1 to either the standard-of-care mental health services (screening, referral, etc.) plus the Youth Friendship Bench SA intervention or standard-of-care services alone. Participants receiving the Youth Friendship Bench SA will complete individual counseling sessions at Enrollment, Week 2 (option to be conducted remotely), Week 4, Week 8 (option to be conducted remotely), and Week 12. They will also be invited to participate in an in-person or virtual group-based session (between their Week 8 and 12 visits, with the exact timing depending on participant availability and participant accrual rate) focused on an economic empowerment activity like job and school applications. Participants in the standard-of-care arm will complete visits at Enrollment, Week 4, and Week 12. The co-primary outcomes are: 1) the proportion with PrEP adherence measured by TFV levels detected in urine using a POC assay at Week 12 and 2) the proportion with reduced symptoms of common mental disorders measured by the SRQ-20 at Week 12. For the PrEP adherence measure, we will utilize urine TFV levels to assess PrEP dosing in the prior 4-7 days. The assay uses a threshold

of 1500 ng/mL to categorize participants as adherent as this was associated with daily dosing over 4-7 days in directly observed therapy.¹¹²

We will conduct all randomizations using a SAS-based computer-generated randomization scheme developed by the study data manager. The site sub-investigator will conduct the randomizations and fill out a randomization log which will be reviewed by the study data manager during visits to the study site. The identity of participants in each of the arms will not be known to investigators and access to the randomization code will be strictly controlled. The study blind will be broken only on completion of the clinical study and after the database has been locked. The study investigators will receive the unblended results only after that point.

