Appendix 4: Schedule of Study Visits and Procedures

	ENROLLMENT	WEEK 2	WEEK 4	WEEK 8	WEEK 12			
Administrative and Behavioral Evaluations/Procedures								
Informed Consent	X							
Collect/update locator information	X		x					
Apply inclusion/exclusion criteria, including the SRQ-20	X							
Randomization	X							
Collect demographics, behavioral, and psychosocial data, including the SRQ-20	X		x		Х			
PrEP adherence assessment via self-report			x		X			
Youth Friendship Bench SA counseling	X	X1	x	X1	Х			
Standard-of-care mental health service delivery	X		x		Х			
Assess any SAEs		x	x	X	X			
Laboratory Evaluation/Procedures								
Urine sample collection for TFV testing using a point-of-care assay			X		X			
PrEP counseling based on urine TFV drug levels			x		Х			

TFV=tenofovir; PrEP=pre-exposure prophylaxis; SAE=serious adverse event; SRQ-20=self-reporting questionnaire 20-item ¹Youth Friendship Bench SA sessions could be conducted remotely via phone

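### Self-harm, the only adverse event of special interest, has no uniform dated question at follow-up and, when not serious, no express route to the DSMB or IRB

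*Protocol*

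**What the plan says.** **Status.** Protocol 9.3 states that "only serious adverse events (SAEs) and adverse events of special interest (AESIs) will be recorded" and that "AESIs are considered reports of self-harm or self-injury". No other AESI is defined. The same section has both classes summarized by arm as a secondary outcome. Sections 6.2 and 11.2.3 list them as a secondary objective and endpoint, and SAP Secondary Analysis 5 plans descriptive statistics and chi-squared tests between groups such as study arms.

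**Collection.** The safety row of Appendix 4 reads "Assess any SAEs" and is marked at Weeks 2, 4, 8 and 12. The termination step in 8.3.6 also records serious events only. Section 9.1 (the part headed 5.1.1) and Appendix 2 add three questions for any woman who endorses SRQ-20 item 17, which concerns thoughts of ending her life. One of the three is "Have you ever tried to kill yourself". For Weeks 4 and 12, 9.1 says "We will follow similar procedures as described for items a-c above". Appendix 1 reproduces the primary care guideline assessment: two mood questions and, after a yes to either, a list of features over the last two weeks. One of those features covers self-harm or suicide, whether in thought or in act.

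**Review.** Section 9.3 states "Site staff will also report information regarding SAEs to their IRB or other local regulatory agencies". Section 9.5 schedules one DSMB meeting before activation and one data review once at least half the participants are enrolled. The data listed for that review are enrollment characteristics, including "referrals for additional mental health services, retention, and social impact or SAE reporting". Section 11.1 adds "The study blind will be broken only on completion of the clinical study and after the database has been locked".

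**The concern.** A safety class that is singled out, recorded and compared between arms needs two things: a question put in the same way, over the same period, to every woman in both arms, and a stated path to someone independent while the trial is running. The visit procedures and reporting sentences provide both for SAEs and neither expressly for AESIs.

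Two things are at stake. The final by-arm table of self-harm could mislead, because what gets recorded depends on gates, on recall windows and on how often each arm is seen. And self-harm that falls short of the SAE criteria might be seen by no DSMB or IRB until the final report, in a population enrolled because of mental health symptoms.

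**Working it through.** No stated figure needs reproducing. The check sets the sections side by side, with a little arithmetic.

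**1. What could pick up a self-harm act during follow-up?**

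| Source | Who is asked at Weeks 4 and 12 | Time window | Acts? |
|---|---|---|---|
| SRQ-20 item 17 (Appendix 2) | Everyone | None printed | No, thoughts only |
| Three follow-up questions (9.1, Appendix 2) | Only those who endorse item 17 | One undated, one current, one lifetime | Suicide attempt only, lifetime |
| Guideline feature list (Appendix 1) | Only those with a yes to a mood question, if the full assessment is done | Last 2 weeks | Yes |
| Question on change (Figure 1 footnote, 7.1) | Everyone | Since last visit | Not named |
| SAE assessment (Appendix 4, 8.3.6) | Everyone | Not stated | Only if serious |
| Interim contacts (8.3.7) | Only those who make contact | n/a | If volunteered |

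No row is ungated, dated and about self-harm or self-injury acts.

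**2. Coverage of the one dated item that names acts.** Follow-up is 12 × 7 = 84 days. Two assessments with 14-day recall cover 2 × 14 = 28 days, and 28/84 = 33%. Sections 8.3.4 and 8.3.6 give every participant the guideline assessment at Weeks 4 and 12. Section 7.1 and the Figure 1 footnote describe those visits as a brief question on whether symptoms have changed. If the brief version is what happens, dated coverage is 0%.

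**3. Assessments by arm.** Appendix 4 marks the SAE row at Weeks 2, 4, 8 and 12. Under 8.3.3 and 8.3.5, only intervention-arm women attend Weeks 2 and 8. That gives 4 scheduled assessments in the intervention arm and 2 in standard of care.

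**4. What counts as an event.** Section 9.3 defines AESIs as reports, with no onset date. Neither 9.3 nor the SAP says which answer creates an AESI record. Gating and short recall push toward undercounting. The lifetime question could let a pre-study attempt in. A woman who denies item 17 at screening is not asked the three questions, may enroll, and may endorse item 17 later. Extra visits could raise the intervention arm's count. The documents give no self-harm rate, so neither the size nor the net direction of the error can be calculated.

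**5. Routing.**

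| Class | IRB | DSMB data review |
|---|---|---|
| SAE, including self-harm that meets SAE criteria | Named (9.3) | Named (9.5) |
| Social harm | Named if serious or unexpected (9.4) | Social impact named (9.5) |
| Self-harm not meeting SAE criteria | Not named | Not named |

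**6. Timing of the one scheduled data review.** Half of 110 is 55, a minimum because 9.5 says at least half. At 9–10 enrolled per month (11.3), this falls at 55/10 = 5.5 to 55/9 = 6.1 months. Assuming steady accrual and no dropout, women past Week 12 by then:
- taking 12 weeks as 3 months: 55 − 3×10 = 25 to 55 − 3×9 = 28;
- taking it as 84/30.4 = 2.76 months: 55 − 27.6 = 27 to 55 − 24.8 = 30.

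So about 25–30 women have completed follow-up. No later review is scheduled for the remaining 110 − 55 = 55; further meetings are ad hoc.

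**The case against.** A reader might infer three stronger things. The documents support none of them.

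*That item 17 is the only probe.* It is not. The guideline list names acts, has a time window and is gated on mood rather than on suicidal thoughts; 8.3.4 and 8.3.6 say everyone receives the guideline assessment. Interim reports are recorded too. The PHQ-9 is collected (10.1), but neither its items nor any link to AESI recording is given. The CRFs are not available, so a missing CRF question cannot be proved. What remains is that no uniform dated question is described and that the sections conflict on the guideline item.

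*That the count is shown to be wrong.* No section turns a lifetime yes into an AESI record. The three questions are there to judge intent, link women to care and decide eligibility. Section 7.3.3 excludes women who report suicidal intent or self-harm, and the Appendix 2 note defers those who endorse any of the three, which narrows the pool with a past attempt. The count is at risk; an error is not demonstrated.

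*That the signal reaches no independent body.* Self-harm that is fatal, life-threatening or leads to hospitalization is an SAE and reaches both bodies. The DSMB's remit is safety data generally, it sees referrals, it may meet ad hoc, and its charter is still to be written. Only non-serious self-harm lacks an express route. An unwritten charter is a reason to name AESIs now.

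Two lesser readings also go too far. Section 12.1.4 lists worsening symptoms among several risks and does not rank it as the main one. The blinding sentence in 11.1 sits among sentences about investigators, so reading it as barring the DSMB is inference. A clarifying clause is enough.

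**Conclusion.** The concern holds in a limited form. Self-harm is the trial's only AESI and a by-arm secondary endpoint, yet no section describes an ungated, dated question on acts, a scheduled AESI assessment or a rule for what counts. Dated coverage is at most 28 of 84 days for women who pass the mood gate, and possibly none. Scheduled safety contacts are 4 against 2 by arm. The resulting comparison is unreliable, and the direction of error is unknown. Self-harm below the SAE threshold is not expressly sent to the IRB or to the one scheduled DSMB data review, which takes place when about 25–30 women have finished follow-up.

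This rests on the protocol and SAP text as written. CRFs, operating procedures or the DSMB charter could close part of the gap, but they are not in these documents. The change should be made; it does not call the primary analyses into question.

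**What to change.** 1. At Weeks 4 and 12, ask every woman in both arms, whatever her item 17 or mood answers, one dated question on self-harm or self-injury since the last visit common to both arms (enrollment or Week 4). State in 9.3 and SAP Secondary Analysis 5 that only events dated after randomization count as AESIs.
2. Add AESI assessment to Appendix 4 and 8.3.6. Base the by-arm comparison on the Week 4 and Week 12 assessments, and list reports from Weeks 2 and 8 or interim contacts separately. Simply widening the existing SAE row would carry the 4-against-2 imbalance into the AESI count. Recall back to the last common visit spans the whole of follow-up in both arms.
3. Name AESIs beside SAEs in the IRB sentence of 9.3 and in the DSMB data list of 9.5, by arm in a closed report. Add a clause to 11.1 that the blinding sentence does not restrict the DSMB.
4. Reconcile 7.1 and the Figure 1 footnote with 8.3.4 and 8.3.6 on what is asked at Weeks 4 and 12. Which version applies is for the investigators to decide.

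The cost is one CRF item, a handful of wording changes and a few more reports to process. No visits or staff are added.

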10.0 DATA COLLECTION

10.1. Quantitative data collection

Demographic and behavioral data will be collected, including information on symptoms of common mental disorders, drug and alcohol use, GBV, post-traumatic stress symptoms, coping behavior, self-esteem, sexual relationship power, and sexual behavior (e.g., number of partners, vaginal sex with partners).

We will access the participant's clinic record to obtain information on age, HIV status, and PrEP status at screening. We will also abstract information on PrEP refills (bottle dispensed, dates of dispensation, and PrEP terminations) from the clinic records during the participant's three-month follow-up period.

Symptoms of common mental disorders will be assessed using the SRQ-20, which will be interviewer-administered by the lay counselors at enrollment, Week 4, and Week 12. Data on depressive symptoms (using the Patient Health Questionnaire-9 [PHQ-9]), anxiety (the Generalized Anxiety Disorder questionnaire [GAD-7]), history of mental health conditions and

services received, drug and alcohol use, GBV, and post-traumatic stress symptoms will also be interviewer-administered on study Case Report Forms (CRFs). All other demographic and behavioral data will be self-collected by participants using a tablet application. Research staff will be available in the clinic to provide guidance and assistance in completing the questionnaire as needed. De-identified data will be collected using REDCap and stored on a secure server.

